9.2. Secondary Efficacy Analyses

Secondary efficacy analyses of hepatic biochemistry and function parameters as described in [Section 5.2.2](#) will be summarized by treatment group using descriptive statistics at Baseline and at each scheduled DB post-Baseline visit. The change from Baseline will also be summarized. Hepatic biochemistry and function parameters will be analyzed using the same ANCOVA model as specified for the primary efficacy analysis.

9.2.1. ALP Responders

ALP response rates, defined as ALP to $<1.5 \times \text{ULN}$, will compare OCA treatment groups vs. placebo at Baseline and all DB post-baseline visits using a Cochran-Mantel-Haenszel test stratified by the randomization stratification factor. For this analysis, missing values will be imputed as described in [Section 3.2.1](#).

The proportion of responders will be summarized by treatment group and visit as described in [Section 6.2.2](#) for W24C, W12C, and ITT populations.

9.2.2. Hepatic Biochemistry and Indices of Function

The secondary efficacy parameters related to hepatic biochemistry and are described in [Section 5.2.2](#).

These parameters will be analyzed using arithmetic summary statistics, ANCOVA, and model estimates with independent variables as described [Section 6.2.3](#) for the primary efficacy endpoint.

9.2.3. Markers of Hepatic and GI Inflammation, Disease, and Fibrosis

The secondary efficacy parameters related to markers of hepatic and GI inflammation and disease include calprotectin, CRP, CK-18, IgA, IgG, IgM, IL-6, IL-12, IL-23, TGF- β , and TNF- α .

The secondary efficacy parameters related to measures of fibrosis include hepatic stiffness measurements obtained via TE (at participating sites), the ELF score and its components (HA, P3NP, T1MP-1).

These parameters will be analyzed using arithmetic summary statistics, ANCOVA, and model estimates with independent variables as described in [Section 6.2.3](#) for the primary efficacy endpoint.

The proportion of fibrosis improvement based on TE measurement will be summarized using arithmetic summary statistics as described in [Section 6.2.2](#) by treatment group at Week 24 of the DB phase. Fibrosis improvement rates, any improvement vs. no improvement or worsening, will compare OCA treatment groups vs. placebo at Week 24 using a Cochran-Mantel-Haenszel test stratified by the randomization stratification factor.

Fibrosis improvement will also be defined as follows:

- Any improvement (Change from Baseline <0)
- No change or Worsening (Change from Baseline equal to ≥ 0)

Calprotectin will potentially be analyzed. The details of the analysis will be specified in a separate SAP.

9.2.4. PK and PD Concentrations

Unconjugated OCA, glyco-OCA, and tauro-OCA will be summed to create total OCA concentration. Concentrations will be converted from ng/mL units for each analyte to ng-equivalence of OCA/mL units using the following molecular weights (MW): unconjugated OCA = 420.6 g/mol, glyco-OCA = 477.7 g/mol, and tauro-OCA = 527.8 g/mol. The PK Population will be used in the analysis of PK and bile acid data (if performed). Data will be presented to 3 significant figures. The PK and PD analyses are considered exploratory analyses per the protocol.

9.2.4.1. PK Concentrations

The values at Week 12 and Week 24 for OCA (unconjugated), glyco-OCA, tauro-OCA, total OCA, and C4 will be summarized using descriptive statistics as defined in [Section 6.2.1](#) and [Section 6.2.6](#) using both arithmetic and geometric statistics. Plasma concentration data of OCA (unconjugated), glyco-OCA, tauro-OCA, total OCA, and C4 will be listed by subject, nominal sampling time, actual sampling time, and calculated elapsed time. Standard summary statistics will be calculated for concentrations at each time point.

Mean (SD) and median plasma concentration versus time data of OCA (unconjugated), glyco-OCA, tauro-OCA, total OCA, and C4 will be plotted on a linear and semi-logarithmic scale using nominal time. Figures of linear and semi-logarithmic plots will be generated for individual subject plasma concentration versus time using the actual sampling times.

9.2.4.2. PK Parameters

PK parameters will be determined using standard non-compartmental methods. The PK of OCA and its conjugates will be summarized in tabular and graphical forms. The main PK parameters estimated in this study are:

- C_{\max} , (ng/mL): the first observed maximum plasma concentration;
- t_{\max} , (hr[s]): the time after dosing at which C_{\max} is observed; and
- AUC_{0-6} , (hr*ng/mL): area under the concentration-time curve from hour 0 to last post-dose sampling time (hour 6), calculated by the linear trapezoidal method.
 - The linear trapezoidal rule should be used for estimation of AUC
 - Where the clinical pharmacologist identifies that another method is more appropriate, the reason for this decision should be documented
 - At least 3 quantifiable concentration-time values must be available to compute AUC_{last}

Additional parameters may be calculated in order to further characterize the PK of OCA and its conjugates if deemed necessary.

Plasma values below the limit of quantitation (BLQ) for OCA, glyco-OCA, tauro-OCA, and C4 will be imputed to lower limit of quantification (LLOQ)/ 2.

Reporting and Significant Figures: The concentration data as reported by the respective bioanalytical group should be used without rounding for all analysis. The non-compartmental parameters should not be reported to any greater accuracy than that of the concentration data. Default significant figures used for reporting in text and tables of the study report is three significant figures, except for time related parameters (h) and for geometric least square mean ratios. Time related parameters (h) which will be presented with two decimal places. Geometric least square ratios will be presented with two decimal places.

Week 12 and Week 24 AUC₀₋₆ and C_{max} for OCA (unconjugated), glyco-OCA, tauro-OCA, total OCA, and C4 will be summarized using descriptive statistics as defined in [Section 6.2.1](#) and [Section 6.2.6](#) using both arithmetic and geometric statistics. T_{max} will be summarized using just the arithmetic methods described in [Section 6.2.1](#). All PK parameters will be presented in a listing by subject.

9.2.4.3. Bile Acids

Analysis of conjugated and unconjugated bile acids may be undertaken per the protocol.

Bile acids include the following: total bile acids, UDCA (unconjugated-UDCA, glyco-UDCA, tauro-UDCA), chenodeoxycholic acid (CDCA) (unconjugated-CDCA, glyco-CDCA, tauro-CDCA), LCA (unconjugated-LCA, glyco-LCA, tauro-LCA), cholic acid (CA) (unconjugated-CA, glyco-CA, tauro-CA), and deoxycholic acid (DCA) (unconjugated-DCA, glyco-DCA, tauro-DCA).

The bile acid assay comprises 15 sub-component bile acid concentrations that will be used to create totals of the individual bile acid concentrations. Concentrations of the bile acids will be converted to molar units using the molecular MWs of the bile acids. The MWs of the bile acids and their conjugates are presented in [Table 1](#). For each bile acid, the assay will provide 3 subcomponent values that will need to be summed to produce the total bile acid value, as shown below in [Table 1](#). As an example, the total UDCA concentration would be the sum of the glyco-, tauro-, and parent molecules.

Table 1. Bile Acids and Their Sub-Components

| Derived | Sub-Components (Molecular Weight) | | |
|------------|-----------------------------------|-----------------------------|--------------------|
| Total UDCA | Glyco-UDCA (449.6 g/mol) | Tauro-UDCA (499.7 g/mol) | UDCA (392.6 g/mol) |
| Total CDCA | Glyco-CDCA (449.6 g/mol) | Tauro-CDCA (499.7 g/mol) | CDCA (392.6 g/mol) |
| Total DCA | Glyco-DCA (449.6 g/mol) | Tauro-DCA (499.7 g/mol) | DCA (392.6 g/mol) |
| Total CA | Glyco-CA (465.6 g/mol) | Tauro-CA (515.7 g/mol) | CA (408.6 g/mol) |
| Total LCA | Glyco-LCA (433.6 g/mol) | Tauro-LCA (483.7 g/mol) | LCA (376.6 g/mol) |

Individual total bile acids are derived as the sum of all bile acids (total UDCA, total CDCA, total DCA, total CA, and total LCA).

Total endogenous bile acids are derived as the sum of all bile acids, excluding all forms of OCA and UDCA.

Proportions of each bile acid are derived as the individual bile acid total divided by total bile acids (eg, total UDCA/total bile acids).

The PK population will be used to summarize the total bile acid concentrations. The individual bile acids, total endogenous bile acids, and each of the bile acid proportions will be summarized by treatment group using descriptive statistics. Values BLQ will be treated as lower limit of quantification (LLOQ)/2. For total UDCA and total endogenous bile acid, the change from Baseline concentrations within each treatment group will be compared using a paired t-test. Only samples from subjects that have a confirmed fasting (based on eCRF) of approximately 8 hours or more prior to the subject's visit will be included in the analysis. The final determination of subjects included in the PK population and the samples included will be determined prior to database lock of the DB phase.

Reporting and Significant Figures: The concentration data as reported by the respective bioanalytical group should be used without rounding for all analysis. The non-compartmental parameters should not be reported to any greater accuracy than that of the concentration data. Default significant figures used for reporting in text and tables of the study report is three significant figures, except for time-related parameters (h) and for geometric least square mean ratios. Time-related parameters (h) will be presented with two decimal places. Geometric least square ratios will be presented with two decimal places.

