## **7. SELECTION AND WITHDRAWAL OF SUBJECTS**

### **7.1. Subject Population**

Approximately 75 subjects with PSC will be randomly assigned to treatment groups using an interactive web response system (IWRS). Up to 50% of the trial population may be taking concomitant UDCA. Once this cap is reached, only those subjects who have not been treated with UDCA for at least 3 months prior to and including Day 0 may be enrolled. In addition, a maximum of 25% of enrolled subjects will have a total bilirubin between  $>1.5x$  ULN and  $<2.5x$  ULN at Screening. Prospective subjects will be identified primarily from the hospital and/or physician's database of PSC subjects, or may be referred from other physicians. Subjects may self-refer themselves to an Investigator if they become aware of the trial through local, national or international PSC patient societies, forums and networks or websites (eg, [www.clinicaltrials.gov](http://www.clinicaltrials.gov)).

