5.2.6. Pharmacodynamic Bile Acids

The following are PD bile acid endpoints: total bile acids, ursodeoxycholic acid (UDCA), chenodeoxycholic acid (CDCA), lithocholate acid (LCA), cholic acid (CA), deoxycholic acid (DCA), (conjugated and unconjugated forms) and C4 in relation to the average exposure of total OCA.

- Observed values and change from Baseline will be evaluated at each DB post-Baseline visit

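### Bile-acid proportions and the UDCA-inclusive total pool UDCA users with non-users, so they mix the OCA effect with UDCA intake

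*SAP*

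**What the plan says.** SAP 9.2.4.3 defines the total with UDCA inside it: "Individual total bile acids are derived as the sum of all bile acids (total UDCA, total CDCA, total DCA, total CA, and total LCA". The proportions follow from that: "Proportions of each bile acid are derived as the individual bile acid total divided by total bile acids (eg, total UDCA/total bile acids". The same section also defines a UDCA-free quantity: "Total endogenous bile acids are derived as the sum of all bile acids, excluding all forms of OCA and UDCA".

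On reporting, "each of the bile acid proportions will be summarized by treatment group using descriptive statistics". The only formal bile-acid test is within group: "For total UDCA and total endogenous bile acid, the change from Baseline concentrations within each treatment group will be compared using a paired t-test". SAP 9.2.5 plots Week 12 and Week 24 values, and changes from Baseline, of total bile acids and of each acid against total OCA exposure. The endogenous total is not among the plotted variables, and nothing asks for UDCA users to be marked.

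Protocol 7.1 states: "Up to 50% of the trial population may be taking concomitant UDCA". UDCA use is a randomisation stratum and a named subgroup in SAP 6.2.8. In SAP Appendix A, however, the only efficacy table by UDCA use is the one for ALP (14.2.1.9). The PK-population bile-acid tables have no such split.

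**The concern.** In a UDCA user, the denominator of the CDCA, CA, DCA and LCA proportions contains a second administered drug. In a non-user it should contain little or none. Two problems follow.

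First, if the two OCA groups contain different shares of UDCA users, their mean proportions and mean totals differ with no OCA effect at all. Stratified randomisation does not prevent this here. SAP 7.6 limits the population to OCA subjects who consent to PK sampling, and Protocol 10.5 makes that consent optional and available only at selected sites.

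Second, the artefact arises even within one subject whose UDCA is constant. If endogenous acids fall, UDCA becomes a larger share and every endogenous proportion shrinks, although the endogenous mix is unchanged.

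The pooled paired test on total UDCA has a related weakness, because it averages in subjects who are not taking the drug. What is at stake is the reading of OCA's effect on bile-acid composition, and of exposure plots that Protocol 10.5 says should help identify doses. The primary ALP analysis is not touched.

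**Working it through.** The plan states no figure to reproduce beyond a count: "The bile acid assay comprises 15 sub-component bile acid concentrations", which agrees with 5 acids × 3 forms = 15, of which 3 are UDCA forms. The documents give no bile-acid concentrations, no OCA effect on bile acids and no PK-subset size. Everything below is illustration under stated assumptions.

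**Assumptions.** Endogenous pool at Baseline E = 1. CDCA is 40% of it. UDCA is a share s of a user's total (20%, 40% or 60%) and 0 in non-users, so a user's UDCA amount is U = s/(1−s), held constant. OCA lowers all endogenous acids by the same fraction e.

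**1. Within-subject artefact, e = 30%.** After treatment, CDCA/total = 0.40 × 0.70/(0.70 + U).

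| s | U | CDCA/total before → after | UDCA share before → after | Change in user's total |
|---|---|---|---|---|
| 20% | 0.25 | 0.32 → 0.295 | 0.20 → 0.26 | −24% |
| 40% | 0.667 | 0.24 → 0.205 | 0.40 → 0.49 | −18% |
| 60% | 1.50 | 0.16 → 0.127 | 0.60 → 0.68 | −12% |

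For s = 40%: 0.28/(0.70 + 0.667) = 0.205. In a non-user CDCA/total stays at 0.40 and the total falls 30%. CDCA over the endogenous total is 0.40 in everyone, before and after.

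**2. Mix effect with no OCA effect.** With user fraction f, mean CDCA/total = f × 0.40 × (1−s) + (1−f) × 0.40, and mean total = 1 + f × U. Comparing f = 40% with f = 60%:

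- s = 20%: 0.368 v 0.352; mean total 1.10 v 1.15 (5% apart)
- s = 40%: 0.336 v 0.304; mean total 1.27 v 1.40 (11% apart)
- s = 60%: 0.304 v 0.256; mean total 1.60 v 1.90 (19% apart)

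The endogenous total and CDCA/endogenous do not differ between the arms.

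**3. How easily such a mix arises.** With 50% users and no stratification, the exact binomial chance of a gap of at least 20 points in user share between two arms is 39%, 45%, 31% and 20% for 6, 8, 12 and 25 subjects per arm. It is not monotone because the counts are discrete.

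**4. Paired test on total UDCA.** SAP 9.2.4.3 sets values below quantification to LLOQ/2. A non-user below the limit at both visits therefore contributes a change of exactly zero. With equal numbers of users and such non-users, the mean change is half that in users. With d = mean/SD of the change in users, the t-ratio is multiplied by 1/√(1 + d²/2): 0.98 at d = 0.3, 0.82 at d = 1 and 0.69 at d = 1.5. The doubled sample size offsets part of this. Simulated power at two-sided 0.05, for d from 0.3 to 1.5, falls by 0–1 points with 12 users per arm, 1–3 with 8 and 2–7 with 6. With 4 users at d = 1 it drops from 29% to 12%.

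**The case against.** The case against is substantial. The UDCA-free total is already defined, summarised and given one of the only two bile-acid tests. The UDCA-inclusive total and the proportions get no test, so no formal inference is biased. CDCA, CA, DCA and LCA concentrations and C4 are summarised and plotted without UDCA in any denominator. Protocol 8.2.1 holds the UDCA dose constant in the double-blind phase and bars non-users from starting. SAP 5.2.6 says "Observed values and change from Baseline will be evaluated at each DB post-Baseline visit", so subjects largely act as their own control for concentrations. SAP 9.2.4 labels PK and PD exploratory, and SAP 9.2.4.3 makes the bile-acid analysis optional. A share of the whole measured pool is also a legitimate measure; the UDCA share itself needs that denominator.

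A reader might infer that the bile-acid totals and proportions show who takes UDCA rather than what OCA does. The documents do not support that. One of the totals contains no UDCA, and under a real OCA effect the pooled measures still move (the totals in step 1 fall by 12% to 24% in users). The effect is diluted and mixed with UDCA use, not replaced by it.

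Constant UDCA does not rescue the proportions, however: step 1 holds UDCA fixed and the artefact still appears. The exposure plots also include actual values, where users are shifted whatever their OCA exposure. As to status, SAP 5.2 lists bile acids as secondary endpoints and Protocol 10.5 calls the exposure-response work a secondary efficacy analysis, so the exploratory label lowers the priority without removing the point. The test-dilution argument is weak for power unless users are very few; the halved estimate stands if half the subjects are non-users with no change.

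**Conclusion.** A minor point that holds within limits. The bile-acid proportions, the UDCA-inclusive total and its exposure plots combine OCA's effect with UDCA intake, and a uniform fall in endogenous acids would appear in UDCA users as a change in composition that did not happen. The pooled UDCA test estimates an average over takers and non-takers. The endogenous total, the individual endogenous acids and C4 are unaffected.

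The size cannot be derived from the documents. The figures rest on assumed UDCA shares of 20–60% in users and none in non-users, CDCA at 40% of endogenous acids, equal proportional falls and constant UDCA. The direction of the artefact needs only UDCA present in users and falling less, proportionately, than the endogenous acids.

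**What to change.** In SAP 9.2.4.3, keep the share of total UDCA in total bile acids, and add CDCA, CA, DCA and LCA proportions over total endogenous bile acids. Present the proportions and both totals by baseline UDCA use within treatment group. Run the paired test on total UDCA in baseline UDCA users. In SAP 9.2.5, add total endogenous bile acids to the exposure plots and mark UDCA users with a separate symbol. Update the table and figure list in Appendix A to match.

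All of this uses variables the SAP already defines and needs no new data. The cost is some SAP wording, a few extra table columns and plots, and small cells within stratum in an optional-consent subset, so the split tables should remain descriptive.

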9.2.5. Exposure Response of Total OCA to Biomarkers

Scatter plots of the Week 12 and Week 24 actual values and change from Baseline in biomarkers ALP, total bile acids, UDCA, CDCA, LCA, CA, DCA (conjugated and unconjugated forms) and C4 will be created versus total OCA plasma AUC₀₋₆.

9.2.6. Disease-specific symptoms

The Pruritus VAS, Pruritus 5-D Itch questionnaire, Partial Mayo scoring system for assessment of UC activity (partial Mayo score), and Crohn's disease activity index (CDAI) will be compared between OCA treatment groups and placebo at Week 12 and Week 24 using a Wilcoxon rank-sum test. This analysis will be repeated for change from Baseline and percent change from Baseline in these scores.

The proportion of subjects in remission from Crohn's disease (CDAI < 150) will be summarized by treatment group and visit using statistics as described in [Section 6.2.2](#), and compared between treatment groups using Fisher's exact test. The analysis will be repeated for the proportions of subjects in remission from UC (partial Mayo score of ≤ 2 with no individual sub-score exceeding 1), and the proportion with mild disease (a partial Mayo score ≤ 3 with no individual sub-score exceeding 1 point).

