3. STUDY DESIGN AND PLAN

This is a Phase 2, randomized, double-blind, placebo-controlled, dose-finding evaluation of the efficacy and safety of OCA in subjects with PSC. The trial design is shown in [Figure 1](#). Approximately 75 subjects who provide written informed consent and meet all of the inclusion

and none of the exclusion criteria will be randomized to 1 of 3 treatment groups as follows: 1.5 mg titrating to 3 mg OCA, 5 mg titrating to 10 mg OCA, or placebo in a 1:1:1 ratio. Subjects will administer investigational product orally, once daily for 2 consecutive 12-week periods. Randomization will be stratified by the presence or absence of concomitant UDCA use and total bilirubin level ($\leq 1.5 \times \text{ULN}$ or $> 1.5 \times \text{ULN}$ but $< 2.5 \times \text{ULN}$). No more than 50% of subjects randomized will be administering UDCA at the time of randomization.

[figure not shown]
For the first 12 weeks after randomization, the subject's dose will be 1.5 mg OCA, 5 mg OCA, or placebo. After 12 weeks, the subject's dose will be titrated – 1.5 mg OCA titrating to 3 mg OCA and 5 mg OCA titrating to 10 mg OCA – and DB treatment will continue for a further 12 weeks at that dose.

Subjects will have a screening period of up to 30 days prior to Randomization/Day 0. Subjects will attend on site clinic visits at Weeks 2, 6, 12, 14, 18, and 24. The final visit during the DB phase will occur at Week 24, after which subjects will be asked to reconfirm their consent for participation in the LTSE phase (a further 24 months).

Upon a subject's completion of the DB phase, the trial blind will be broken in order to assign the starting OCA dose for the LTSE phase. It is intended that subjects will commence treatment at 5 mg OCA, except those subjects who completed treatment in the DB phase with 10 mg OCA who will continue at 10 mg OCA unless safety and tolerability warrant a dose reduction to 5 mg. The titration schedule and options for the LTSE phase are detailed in the protocol.

The overall study duration is up to 32 months, including up to a 30-day Screening period, 6 month DB period, followed by a 24-month open-label LTSE period, and a 1-month follow-up period. The LTSE may be extended as determined by the sponsor via protocol amendment and regulatory and Institutional Review Board/Independent Ethics Committee review and approval.

Figure 1: Study Design Schematic

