6.2.3. Analysis of Covariance

Analysis of covariance (ANCOVA) will be performed to provide least square (LS) mean estimates and 95% two-sided confidence intervals (CIs) of the change and percentage change from Baseline at each DB post-Baseline visit. Model covariates include then randomization stratification values (ie, UDCA use [yes, no] and screening total bilirubin [$\leq 1.5 \times \text{ULN}$, $> 1.5 \times \text{ULN}$ – $< 2.5 \times \text{ULN}$]) and the Baseline of the parameter being estimated. The primary analysis will exclude the treatment by visit interaction term.

Normality/Equal Variance Testing

The assumption of a random error component being normally distributed will be tested by examining skewness and kurtosis following D'Agostino et al. (1990) with the residuals pooled over treatments. Additionally, homogeneity of variances across treatment groups will be examined using Levene's Test (Glaser 1982) with significance level of 0.05, based on absolute values of the residuals from the residual medians for each treatment. The data will be determined non-normal if the p-value for either the D'Agostino Skewness Test or D'Agostino Kurtosis Test is less than 0.05. If the data do not meet the normality or homogeneity assumptions of the parametric analyses, then a RT-2 rank transformation will be applied to the data (CFB endpoint and baseline value). To minimize the effect of differing study site sizes, the ranks will be standardized to lie between 0 and 1 using the NPLUS1 option of SAS® PROC RANK. Tied values will receive the mean value (midranks) of the corresponding ranks.

Example SAS® code for the primary analysis is as follows:

```
ODS graphics on;  
proc mixed data=ADLB noclprint plots=residualpanel;  
  class ucdafl tbilfl trt;  
  model change=Baseline ucdafl tbilfl trt / ddfm=kr;  
  lsmeans trt / cl diff alpha=0.05;  
  title1 "Linear Mixed Effects Model Based Estimates of XXXX Means";  
  title2 " Fixed Effects for Visit, Randomization Strata, and Treatment and Baseline as  
  Covariates";  
run;  
ODS graphics off;  
quit;
```

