The analysis of time to event will include the number of subjects with the event (first onset, first moderate or severe, first severe), the number of subjects without the event (censored), descriptive statistics of time for those with an event, and range in days for all subjects. Kaplan-Meier (KM) estimates will be calculated by treatment group. The quartiles, including the median time-to-event and their respective 2-sided 95% CIs, will be presented. KM estimates will be plotted as a “survival curve” for each treatment group, with the number at risk identified. The comparison of OCA to placebo will be summarized using a log-rank test stratified by randomization strata factor. The analysis will be repeated on the subset of subjects who experienced a treatment-emergent pruritus event.

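### Pruritus VAS and 5-D Itch are compared by unstratified Wilcoxon tests that use baseline only through change scores; a rank analysis adjusted for baseline and strata would usually be more efficient

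*SAP*

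**What the plan says.** SAP 9.2.6 covers four scores: Pruritus VAS, 5-D Itch, partial Mayo (UC subjects only) and CDAI (Crohn's subjects only). They "will be compared between OCA treatment groups and placebo at Week 12 and Week 24 using a Wilcoxon rank-sum test". The next sentence adds: "This analysis will be repeated for change from Baseline and percent change from Baseline in these scores". No stratification factor or covariate is named, and none of the three versions is designated as the main one.

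The strata are part of the design. SAP 3 states: "Randomization will be stratified by the presence or absence of concomitant UDCA use and total bilirubin level". Other SAP analyses use them:

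- ANCOVA (6.2.3) for ALP, hepatic biochemistry, inflammation and fibrosis markers, and FGF-19: "Model covariates include then randomization stratification values", together with the baseline value ("and the Baseline of the parameter being estimated"). If normality or variance checks fail, change and baseline are both ranked and the model is fitted to the ranks.
- ALP response (9.2.1): "using a Cochran-Mantel-Haenszel test stratified by the randomization stratification factor".
- Time to pruritus as an adverse event (10.3.1): "log-rank test stratified by randomization strata factor".

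SAP 6.2.5 provides Hodges-Lehmann estimates. SAP 6.2.7 places the symptom tests outside the ALP hierarchy, without multiplicity adjustment. Protocol 12.3.2 names no test for these scores.

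**The concern.** Protocol 4.4 names pruritus as the main adverse event related to OCA, protocol 4.5 expects a dose-dependent effect in PSC, and safety is a primary objective. VAS and 5-D are the patient-reported measures of that effect. Pruritus recorded as an adverse event gets a stratified comparison, while pruritus scored by the patient does not, and no reason is given.

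A raw-score test discards baseline. A change-score test subtracts all of it, which adds noise when baseline and follow-up are weakly correlated. Which version does better depends on a correlation that nobody knows beforehand. With three versions, two visits and two dose groups, each score produces 3 x 2 x 2 = 12 comparisons with no stated lead.

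The percent-change version has a further weakness for VAS. SAP 6.3.5 divides by the baseline value, and a VAS baseline of zero is plausible because exclusion criterion 12 removes subjects whose itch needs systemic or enteral treatment. Percent change is then undefined. The 5-D total cannot be zero, since its minimum is 5 (SAP 6.3.6).

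**Working it through.** **Inputs from the documents.** 25 per arm, or 25 x 0.8 = 20 after the 20% dropout in SAP 4; two strata factors; two-sided 5% tests. The only power figure in the documents is for ALP: a difference of 15 with SD 16 and 25 evaluable per arm gives 90.1% by two-sided t-test, in line with the stated 90%. It carries no information about symptom scores.

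**Assumptions, not in the documents.** A treatment difference of 0.7 or 0.8 SD, a baseline to follow-up correlation ρ of 0.3 to 0.8, and strata effects of zero or 0.5 SD each.

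**Step 1: variance.** With equal SDs at both times, variance relative to the raw score is 2(1 - ρ) for change and 1 - ρ² after baseline adjustment. These formulas are exact for means and a guide for ranks.

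| ρ | raw | change | adjusted |
|---|---|---|---|
| 0.3 | 1.00 | 1.40 | 0.91 |
| 0.5 | 1.00 | 1.00 | 0.75 |
| 0.7 | 1.00 | 0.60 | 0.51 |
| 0.8 | 1.00 | 0.40 | 0.36 |

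Change is worse than raw below ρ = 0.5 and better above it. Adjustment is never worse than either, apart from the degrees of freedom it spends.

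**Step 2: simulated power**, 0.7 SD, 25 per arm, no strata effect. The rank ANCOVA uses ranked score, ranked baseline, treatment and two strata terms.

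| ρ | Wilcoxon raw | Wilcoxon change | rank ANCOVA | minus better | minus worse |
|---|---|---|---|---|---|
| 0.3 | 67% | 53% | 69% | +2 | +16 |
| 0.5 | 65% | 65% | 74% | +9 | +9 |
| 0.7 | 64% | 86% | 88% | +2 | +24 |
| 0.8 | 65% | 96% | 96% | 0 | +31 |

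Taking simulations at 20 and 25 per arm together, the difference from the better planned test ranges from about -4 (at ρ = 0.8) to +12 (near ρ = 0.5). Against the worse one it reaches about 36 points.

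**Step 3: if the strata matter.** With 0.8 SD and 20 per arm, gains over the better test at ρ = 0.3, 0.5, 0.7 and 0.8 are about +2, +9, +2 and -1 points with no strata effect. With strata effects of 0.5 SD each they are about +7, +14, +7 and +2.

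**Step 4: validity.** Under no treatment effect, with 0.5 SD strata effects, the Wilcoxon tests rejected in 3.6 to 3.8% of trials and the rank ANCOVA in 4.6 to 5.0%. The planned tests are slightly conservative, not invalid.

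**Step 5: floors.** If about 69% of baselines sit at a floor (assumed), the gain at 25 per arm falls to about 0 at ρ = 0.3 and 3 to 4 points at 0.5 to 0.7.

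**Step 6: small subsets.** The documents do not give the numbers with UC or Crohn's disease. With 8 per arm and 0.8 SD, power for raw, change and rank ANCOVA is 30/24/31% at ρ = 0.3, 28/28/32% at 0.5 and 30/45/44% at 0.7, so differences from the better test are about +1, +4 and -1. At 0.7 SD with 8 per arm, losses reached about 12 points at high correlation. With 12 per arm and 0.8 SD, the gain was about 8 points at ρ = 0.5 (52% against 44%).

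**The case against.** The strongest case for leaving the plan alone has five parts.

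1. **Baseline is already used.** A reader might infer from the first sentence of 9.2.6 that baseline is ignored. The next sentence rules that out, since the test is repeated on change and percent change. What remains is change score against covariate.
2. **The gain is modest and rests on assumptions.** No effect, SD, correlation or power is given for any symptom score, so the documents do not support saying that the trial throws away power it was designed to have. Against the better planned test, the benefit is material only around ρ = 0.5 or if the strata are prognostic. The reply that stands is that the better test cannot be identified beforehand, and the rank ANCOVA is at or near the best throughout the range.
3. **Eligibility compresses baselines.** Exclusion criterion 12 removes subjects with treated itch, so floors and ties are likely. This stands and shrinks the gain.
4. **Pruritus is not judged on these tests alone.** SAP 10.3.1 also plans incidence, event days by severity, Kaplan-Meier curves and a stratified log-rank test. This stands and limits the consequence.
5. **Adjustment could hurt in small subsets.** A reader might want all four scores changed. Step 6 does not support that for partial Mayo and CDAI. Sparse cells add to the problem even in the full trial: the 25% bilirubin cap allows about 25 x 0.25 = 6 subjects per arm in the upper stratum, or about 3 once halved by UDCA use.

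Nor is every other SAP comparison adjusted. The remission proportions in 9.2.6 use Fisher's exact test, and bile acids get a within-group paired t-test (9.2.4.3). The contrast is with the ANCOVA, Cochran-Mantel-Haenszel and log-rank analyses only.

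**Conclusion.** The point holds as a minor matter of efficiency for Pruritus VAS and 5-D Itch. Under an assumed 0.7 SD difference and 20 to 25 per arm, a baseline- and strata-adjusted rank analysis is worth about -4 to +12 points of power against the better of the raw and change tests, and up to about 36 against the worse. Prognostic strata would raise the gain and floored scores would lower it. The planned tests control type I error and are secondary, so no conclusion about ALP is affected. The documents do not support a claim that the tests are invalid or that a stated power is lost.

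**What to change.** In SAP 9.2.6, for Pruritus VAS and 5-D Itch only, name as the lead comparison at each visit a rank ANCOVA of the ranked score on ranked baseline, treatment, UDCA use and bilirubin stratum, with a rule fixed before unblinding for pooling sparse strata. This adapts 6.2.3 rather than copying it, because that section ranks the change from baseline and does so only after a failed assumption check. Keep the Wilcoxon tests as supportive and report Hodges-Lehmann estimates (6.2.5) for the size of the difference. Leave the Wilcoxon test for partial Mayo and CDAI.

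The cost is SAP wording and a little programming. Since protocol 12.3.2 names no test for these scores, a protocol amendment appears unnecessary. The downside is a slight loss of power if the baseline correlation turns out to be very high.
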